3 INVESTIGATIONAL PLAN

3.1 Overall Study Design and Plan

The present study is designed as a Phase II, open-label study of patients with dementia to evaluate potential efficacy of NE3107 using serological measures of insulin resistance, cognitive performance testing, AD biomarkers, and neuroimaging endpoints. Baseline and outcome measures in this study utilize validated tests that are appropriate for repeated measures which are not affected by practice effects. Advantages of this study include the fact that the neuropsychological testing instruments and advanced MRI imaging protocols that have been in routine clinical deployment provide for a high degree of availability and reliability for diagnosis and for monitoring change of status. The study population is sufficiently broad and the conditions of interest are sufficiently prevalent so that recruitment of the projected numbers of participants is not a limiting factor.

The duration of treatment is 3 months. The rationale for 3-month administration is to allow sufficient time for detectable change to occur. To minimize risk, participants will be called within 24 hours following initiation of the drug and weekly thereafter, as well as attend monthly visits the principal investigator to evaluate for safety and tolerability of the study intervention. Mild, moderate, and severe adverse reactions will be reported on an ongoing basis. Previously observed adverse reactions are listed in Table 22 of the Investigator's Brochure. Participants will be discontinued if they have moderate or severe adverse reaction ratings according to the ICH SAE E2A.

(See Appendix 1, Study Events Table.)

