5.1.2 Placebo or Control

All participants will receive the study drug; this study will utilize no placebo group.

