5.5 Blinding

No blinding procedures will be utilized.

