6 STUDY PROCEDURES

For this Phase II open label study, all participants will be screened following acquisition of a signed, written informed consent form.

Screening will involve confirmation that all inclusion criteria and none of the exclusion criterion are met. Following confirmation of inclusion and exclusion criterion, participants will undergo baseline testing to include the following: Advanced magnetic resonance imaging (MRI) of the brain, lumbar puncture, APoE genotyping, cognitive testing, and serological analysis.

All patients will have an advanced MRI of the brain to include T1 and T2-weighted structural images, susceptibility-weighted imaging, neuromelanin, arterial spin labeling (ASL) perfusion, blood oxygen level-dependent (BOLD) at rest, diffusion tensor imaging with neurite orientation density and dispersion (DTI-NODDI), and magnetic resonance spectroscopy (MRS) of the precuneus. MRI will demonstrate if patients have tumors, hydrocephalus, subdural hematomas and other structural etiologies of cognitive decline. Having the scan completed will be required for inclusion, but no specific imaging parameters will determine inclusion. The advanced MRI of the brain will be repeated upon completion of the 3-month study intervention period.

All patients will have APoE swab testing and a lumbar puncture for A β 42 and Tau proteins for Alzheimer's Spectrum. This spinal fluid examination has been shown to be both sensitive and specific for Alzheimer's disease. Cerebrospinal fluid (CSF) studies have demonstrated good sensitivity and specificity for mild cognitive impairment (MCI) and dementia of the Alzheimer's type. MRI volumetrics, perfusion scans and MR spectroscopy have shown to be responsive to change as patients progress from MCI to dementia. The lumbar puncture is performed at entry and after completion of the study protocol. The APoE testing will only be performed at baseline.

Baseline and completion (3-month) cognitive testing will include the Quick Dementia Rating System (QDRS), estimated clinical dementia rating (CDR) scale level, Mini-Mental Status Evaluation (MMSE), Montreal Cognitive Examination (MoCA), and Alzheimer's Disease Assessment Scale (ADAS-Cog12). Upon completion of the protocol intervention, participants will also be asked to report a Global Rating of Change (GRC) score in addition to the neuropsychological testing battery.

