9.5.2 Statistical Considerations for Secondary Endpoints

Secondary endpoints will include a longitudinal comparison of metabolic and serological analysis (specifically measures of glucose and insulin homeostasis); the level of cognitive impairment as defined by neuropsychological testing (QDRS/CDR, MMSE, ADAS-Cog, and MoCA scores). Thresholds for reporting clinically meaningful change will include references to published minimal clinically important differences (MCIDs) for each measure. Paired samples t-tests will be used to statistically analyze each secondary endpoint, including the cognitive measures described below as well as changes in serological markers.

The ADAS-Cog evaluates participants' cognitive abilities. It is composed of 11 parts that measure word recall, object/figure naming, command following, constructional praxis, ideational praxis, orientation, word recognition, test direction recall, spoken language, comprehension, and word-finding difficulty. The ASAS-COG is scored from 0-70 by measuring the errors made in each task, with a score of 70 representing the most severe impairment. A point reduction of 3.1 to 3.8 has been found to be the minimal clinically important difference (Schrag & Schott, 2012).

The MMSE is a 30-point questionnaire that evaluates cognition. The MMSE includes specific tasks that assess orientation, attention, memory, language and visual-spatial skills. MMSE scores range from 0 – 30 possible points; 0-17: severe cognitive impairment, 18-23: mild cognitive impairment, 24-30: no cognitive impairment. A point decrease \geq 3 on the MMSE has been identified as the minimally clinically important difference (Andres, 2019).

The MoCA evaluates frontal-executive functions (e.g., verbal abstraction and mental calculation), language (e.g., confrontation naming, phonemic fluency), orientation (e.g., person, place, date, day of the week, and time), visuospatial construction (e.g., simple figure copy), divided visual attention, and immediate and delayed memory of unstructured information (Nasreddine, Phillips, Bédoré, Charbonneau, Whitehead, Collin, et al., 2005). MoCA scores range from 0-30 possible points; 26 or greater is considered to reflect normal cognitive status.

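### Section 3.1 asserts without support that the outcome measures are free of practice effects, yet no alternate forms are specified for MoCA, MMSE or ADAS-Cog12, so a retest gain in this single-arm trial cannot be separated from a drug effect

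*Combined protocol and SAP*

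**What the plan says.** Protocol section 3.1 says that the baseline and outcome measures are validated tests, suited to repeated use, "which are not affected by practice effects". No reference or data accompany the sentence.

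Section 6 sets the repeat testing: "Baseline and completion (3-month) cognitive testing will include the Quick Dementia Rating System (QDRS), estimated clinical dementia rating (CDR) scale level", followed by MMSE, MoCA and ADAS-Cog12. Sections 7.1 and 7.5 list MoCA, MMSE and ADAS-Cog12 again, at baseline (Days -10 to -1) and at Day 90 ± 15. They name the tests but not the version or form.

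Section 9.5.2 describes the content. The ADAS-Cog parts begin with "word recall, object/figure naming, command following" and go on to include word recognition. The MMSE is said to assess memory among other domains. The MoCA covers "immediate and delayed memory of unstructured information". The same section assigns a paired t-test to each secondary endpoint, the cognitive measures included, and says that change will also be read against published MCIDs.

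On design, section 5.1.2 says "All participants will receive the study drug; this study will utilize no placebo group", and section 5.5 says "No blinding procedures will be utilized".

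**The concern.** A test of recall or recognition can be done better the second time because the person has met the items or the task before. A concurrent control group tested on the same schedule would show the same gain, and the comparison would remove it. This trial has no such group. The paired t-test takes the whole mean change, whatever its source, and compares it with zero.

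The sentence in 3.1 tells the reader that one of the main rival explanations for a cognitive gain is absent. Nothing in the documents supports it, and the item content listed in 9.5.2 gives reason to doubt it for the three performance tests.

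The stake is what may be concluded about cognition. Sections 2.2 and 9.5.2 rank it as secondary, but section 6 names neuropsychological testing together with MRI when it describes the primary endpoints, and section 9.5.1 correlates cognitive change with imaging change. A retest component would carry into those correlations too.

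**Working it through.** **1. Is there anything in the plan that would remove a retest gain?**

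- Alternate forms or rotation of word lists: none specified in 6, 7.1, 7.5 or 9.5.2.
- Second pre-treatment baseline or practice session: none described.
- Concurrent control: none (5.1.2).
- Z-scores against published normals (9.5.1): these place a participant in a reference population. No retested normal group is described, so they do not estimate a retest gain.
- Expected progression of 4-9% over 3 months (9.5): this is one quarter of the annual 15-35% (15/4 = 3.75; 35/4 = 8.75). It is a proportion progressing, not a mean change on a scale, and the paired t-test does not use it.
- Other models: 9.1 names MMRM and 9.5.1 repeated-measures ANOVA. In one arm with one baseline and one follow-up, their time effect is again the mean change from baseline, so the issue is the same.

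The retest interval runs from 75 + 1 = 76 days to 105 + 10 = 115 days.

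**2. Inputs for the size**

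- Completers: 20 (9.2). The plan's enrolment figure reproduces: 20/(1 - 0.20) = 25.
- Significance level: 0.05 (9.1). Sidedness is not stated; two-sided is assumed.
- Retest gain and SD of change: not given. The net drift d = (mean change with an inert drug)/(SD of change) is therefore assumed over a range, with positive values meaning improvement.

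**3. Formula**

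Under an inert drug the paired t statistic is noncentral t with n - 1 = 19 degrees of freedom and noncentrality d × √20. The two-sided critical value is 2.093. The chance of a significant improvement is the upper tail, P(T > 2.093). For d = 0.2 the noncentrality is 0.2 × 4.472 = 0.894, and the tail is 0.133.

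**4. Results, one scale, 20 completers**

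| Net drift d (assumed) | Chance of a significant improvement |
|---|---|
| -0.2 | 0.2% |
| -0.1 | 0.9% |
| 0 | 2.5% |
| 0.1 | 6.2% |
| 0.2 | 13.3% |
| 0.3 | 24.6% |
| 0.4 | 39.7% |

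The right benchmark is 2.5%, the improvement half of a two-sided 5% test. If all 25 participants complete, d = 0.3 gives 30.2%: a larger sample makes a positive drift more likely to reach significance.

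In points, with an assumed SD of change of 3 to 5, a net gain of 1 point (d = 1/3 to 1/5) gives 29% down to 13%.

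**The case against.** Several stronger readings are tempting, and the documents do not support them.

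- A reader might infer that the same forms are reused. The plan does not say so. It is silent on versions, and section 10.7 mentions examination packets whose content is not shown.
- A reader might infer that the plan will report a retest gain as a drug effect. A paired t-test attributes nothing, section 3.1 speaks only of potential efficacy, and 9.5.2 adds MCIDs as a second yardstick. An average gain of 1 point would fall well short of the 3.1 to 3.8 points cited for the ADAS-Cog. The MCIDs do not subtract a retest gain, however.
- A reader might infer that freedom from practice effects is the reason for having no control. No section says this. Section 3.2, whose heading promises the rationale for the control group, discusses dose only.
- A reader might take the point to cover all cognitive scales. Section 9.5.2 says that QDRS is a caregiver interview and that CDR is converted from it. Participant learning does not reach either by this route.
- A reader might conclude that an inflated error rate has been shown. It has not. The drift is assumed, and in a CDR 0.5 to 1 population, decline over 3 months could cancel a retest gain or outweigh it. The negative rows of the table are then the relevant ones.

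It is also fair to say that 9.1 has a testing-order rule, while the figures above are for one scale before that rule. No order is given. For whichever scale comes first in its family the rule changes nothing; for later scales the figures are upper limits. Ordering cannot protect against a mean change that is not zero under an inert drug.

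What stands is the unsupported assertion, the missing specification of forms, and the lack of any means to separate learning from drug effect.

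**Conclusion.** The point holds as one of specification and interpretation for MoCA, MMSE and ADAS-Cog12. The assertion in 3.1 has no support in the documents, and the plan neither reduces nor measures a retest gain on these three tests.

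The size is unknown. The range of 0.2% to 40% is a sensitivity analysis, not an estimate. It rests on 20 completers, a two-sided 0.05 test, normally distributed change scores, an inert drug, and a net drift between -0.2 and 0.4 SD of change that the documents neither give nor exclude. The net direction cannot be settled from the plan. That is itself a reason not to state that the effect is absent.

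The absence of a control arm is a declared design choice and is not what this point asks to change.

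**What to change.** 1. In sections 6, 7.1 and 7.5, specify equivalent alternate forms or word lists for MoCA, ADAS-Cog and the MMSE recall items, with the order of forms balanced across participants. Record the form used at each visit.
2. Delete the assertion about practice effects from 3.1.
3. State in 9.5.2 that a cognitive gain in this single-arm trial cannot be separated from retest effects.

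The cost is protocol wording and a form-order list, with no added participants, visits or procedures. The downside is some extra noise from small differences between forms. The benefit is partial: alternate forms reduce learning of specific items, but leave familiarity with the task and open-label expectation in place. The limitation statement is therefore needed as well as the forms.

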6.9 Adverse Events Assessments

Following all of the inclusion/exclusion criteria may help to reduce the occurrence of severe adverse reactions. Both the principal investigator and sub-investigators are medical doctors, and are licensed in the state of California, and are in close communication the primary IND holder (BioVie, Inc.) regarding safety monitoring. We will be performing routine patient calls and standard monitoring of side effects due to these medications, as discussed elsewhere in this report. Following these guidelines, side effects can be identified early enough to mitigate any significant or permanent side effects.

6.9.1 *Timing*

NE3107 has no specific dose-limiting toxicity to guide stopping criteria for laboratory values for safety monitoring. Abnormal lab values will be reviewed in the context of patient safety and potential relationship with NE3107 treatment and NE3107 prior safety data. The investigator may terminate a patient's participation in the trial due to abnormal lab values irrespective the lab values potential relationship with NE3107 treatment.

6.9.2 *Severity*

The term "severe" describes the intensity (severity) of a specific event; the event itself, however, may be of relatively minor medical significance (such as severe headache). This means it is not the same as "serious", which is based on patient/event outcome or action criteria usually associated with events that pose a threat to a patient's life or functioning.

The severity of all AEs will be graded by the PI/Sub-Investigator or a medical qualified delegate according to the following definitions:

Mild: Adverse event resulting in discomfort, but not sufficient to cause interference in normal daily activities.

Moderate: Adverse event resulting in discomfort that is sufficient to cause interference in daily activities.

Severe: Adverse event resulting in discomfort causing an inability to carry out daily activities.

6.9.3 *Relationship*

The PI/Sub-Investigator will assess the relationship of all adverse reactions to NE3107 using the following scale:

Probable: A clinical event, including laboratory test abnormality, with a reasonable time sequence to drug administration, unlikely to be attributed to concurrent disease or other drugs or chemicals, and which follows a clinically reasonable response on withdrawal.

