Possible: A clinical event, including laboratory test abnormality, with a reasonable time sequence to drug administration, but which could also be explained by concurrent disease or other drugs or chemicals. Information on drug withdrawal may be lacking or unclear.

Unlikely: A clinical event, including laboratory test abnormality, with a temporal relationship to drug administration which makes a causal relationship improbable, and which other drugs, chemicals or underlying disease provide plausible explanation.

Unrelated: This category is applicable to AEs which are judged to be clearly and incontrovertibly due to extraneous causes (diseases, environment, etc.) and do not meet the criteria for drug relationship listed for the above-mentioned conditions.

All AEs will be evaluated by the PI/Sub-Investigator, who must approve the subject for subsequent dosing.

Any AEs, whether serious or non-serious, will be monitored throughout the study and followed to resolution, when possible, regardless of whether the subject is still participating in the study.

6.9.4 *Expectedness*

The principal investigator and study doctor will be responsible for determining whether an SAE is expected or unexpected as per drug labels. An adverse event will be considered unexpected if the nature, severity, or frequency of the event is not consistent with the risk information previously described for the intervention.

6.9.5 *Clinical Significance*

Clinical laboratory data collected during the course of the study, which exceeds or drops below the acceptable limits for the participant population and which, based on baseline values, are considered by the Investigator to be clinically significant, will be reported as an AE. If clinically significant abnormal laboratory values lead to, or are associated with clinical symptom(s), they will be reported as an AE.

6.9.6 *Serious Adverse Events*

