6.11 Removal of Participants from the Trial or Study Drug

The investigator may withdraw a subject from trial participation for any of the following reasons:

- A protocol violation occurs,
- A serious or intolerable adverse event occurs,
- A clinically significant change in a laboratory parameter occurs,
- The sponsor or investigator terminates the study, or
- The subject requests to be discontinued from the study.

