7.3 Treatment Period (Day 1 to Day 90)

The drug under investigation is NE3107 (17a-ethynyl-androst-5-ene-3b,7b,17b-triol). NE3107 is formulated with common excipients used in oral medications in #2 hard gelatin capsules. The capsules are designed for oral administration. NE3107 capsules are stable at room temperature for at least 18 months. Stability of the capsules used in this study will be monitored by a concurrent stability study conducted by the capsule manufacturer and the holder of the primary IND, Biovie, Inc (Santa Monica, CA).

The rationale for 3-month administration is to allow sufficient time for detectable change to occur. To minimize risk, participants will be called within 24 hours following initiation of the drug and weekly thereafter, as well as meet with the study doctor 1 week after starting the NE3107 regimen and attending once-monthly visits thereafter with the principal investigator to evaluate for safety and tolerability of the study intervention for the duration of the study protocol. These visits will include evaluations of the following:

- Vital signs
- Height, weight, and calculation of BMI
- Documenting changes in concomitant medications
- Participant reports of tolerability
- Evaluation for AEs
- Assessing compliance with the study drug

Additionally, specific laboratory tests will be repeated at weeks 2, 4, and 8 to ensure safety (**6.6.1 Laboratory Parameters**). Mild, moderate, and severe adverse reactions will be reported on an ongoing basis. Previously observed adverse reactions are listed

in Table 22 of the Investigator's Brochure. Participants will be discontinued if they have moderate or severe adverse reaction ratings according to the **ICH SAE E2A**.

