8 QUALITY CONTROL AND ASSURANCE

BioVie Inc. is encouraged to visit The Regenesis Project at their convenience. The Principal Investigator (PI) and study staff will provide upon request source documents and/or other study-related documents. The PI will maintain regular written and telephone communication with BioVie Inc. In addition, to ensure quality data and standardization, The Regenesis Project will send monthly status reports to BioVie Inc.

All data will be recorded in accordance with good clinical practice (GCP) to ensure accuracy, completeness, legibility, and timeliness of the data reported. All data will be recorded directly on the source documents and will be considered source data. This data will be transferred to Case Report Forms (CRFs). Source data and CRFs will be kept on site at The Regenesis Project. All records and documents pertaining to the study will be retained by The Regenesis Project for at least five (5) years from the completion of the study and will be available for inspection by the Sponsor and Regulatory Agencies.

All source documents and laboratory reports will be Quality Control reviewed to ensure accuracy and completeness. Adverse events will be reviewed and assessed for severity according to the ICH SAE E2A, dated 27 October 1994, by the PI. Specific processes of the study, source documentation and case report forms, and any reports will be audited internally within The Regenesis Project and may be subject to audit by BioVie Inc.

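### Sections 3.1, 7.3 and 9.6 make stopping mandatory for moderate or severe adverse reactions, Sections 6.11 and 6.9.3 leave it to the investigator, and no passage says which governs or what discontinued means for follow-up

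*Combined protocol and SAP*

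**What the plan says.** Three sections carry a mandatory rule. Section 3.1 reads "Participants will be discontinued if they have moderate or severe adverse reaction ratings according to the ICH SAE E2A"; Section 7.3 repeats "Participants will be discontinued if they have moderate or severe adverse reaction ratings", and Section 9.6 uses the same sentence.

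Two sections are worded differently. Section 6.11, on removal from the trial or study drug, opens with "The investigator may withdraw a subject from trial participation for any of the following reasons". Its adverse-event item is "A serious or intolerable adverse event occurs"; moderate or severe intensity is not on the list. Section 6.9.3 says "All AEs will be evaluated by the PI/Sub-Investigator, who must approve the subject for subsequent dosing", with no exception by grade.

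On grading, Section 6.9.2 says "The severity of all AEs will be graded by the PI/Sub-Investigator or a medical qualified delegate according to the following definitions" and then defines mild, moderate and severe. It also explains that severe describes intensity and is not the same as serious. Section 8 has adverse events "assessed for severity according to the ICH SAE E2A", and Sections 3.1, 7.3 and 9.6 cite the same guideline.

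On the analysis side, Section 9.2 enrols 25 to obtain at least 20 completers with 20% attrition. Section 9.3 defines a Full Analysis Population (any study drug and at least one post-baseline assessment) and plans to use all available data, but also says that participants with baseline and completed follow-up data enter the final analyses. Section 7.4 offers MRI, cognitive testing and lumbar puncture at early termination to those willing; the required minimum is a clinical evaluation.

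**The concern.** The same reaction can fall under a mandatory rule in one part of the protocol and under discretion in another. The section that site staff would consult for removals does not contain or cross-refer to the mandatory rule.

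The statistical stake is who reaches the analysed set. In a single-arm comparison with baseline there is no control group in which the same selection would occur. If participants who tolerate the drug poorly are stopped, are not assessed afterwards and are then left out as not evaluable, the estimated change describes those who tolerated it. How many are affected depends on which passage is followed and on whether discontinued means leaving drug or leaving the trial. Neither is stated.

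**Working it through.** **1. The passages side by side, by type of event**

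| Event | 3.1, 7.3, 9.6 | 6.11 | 6.9.3 |
|---|---|---|---|
| Drug-related, moderate, not serious, tolerable | Discontinue | Not listed | Investigator approval |
| Drug-related, severe, not serious | Discontinue | Listed only if intolerable; then discretionary | Investigator approval |
| Drug-related, serious, graded at least moderate | Discontinue | Listed; discretionary | Investigator approval |
| Moderate or severe, judged unrelated | Depends on the meaning of reaction | Listed only if serious or intolerable; then discretionary | Investigator approval |

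The triggers cannot be merged by reading severe as serious, because Section 6.9.2 separates the two terms. The third row is the clearest: both sets of passages address that event directly, one as mandatory and the other as optional. The fourth row stays open because Section 6.9.3 applies its relatedness scale, which includes an unrelated category, to all adverse reactions. In that section, reaction does not clearly mean a drug-related event.

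**2. The plan's own figure**

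Enrolment = completers / (1 − attrition) = 20 / (1 − 0.20) = 25, which reproduces Section 9.2. The margin is 25 − 20 = 5 losses from all causes. Section 9.2 does not say whether the 20% includes safety stops.

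**3. Sensitivity of the completer target (illustration only)**

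The documents give neither a moderate-or-severe reaction rate nor a rate of other loss, so both are assumed. Let b be other loss and r the proportion stopped under the mandatory rule and not assessed afterwards. Then p = (1 − b)(1 − r), expected completers = 25p, and P(at least 20) is the upper tail of a binomial(25, p).

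| r | b = 5%: 25p | b = 5%: P(≥20) | b = 10%: 25p | b = 10%: P(≥20) |
|---|---|---|---|---|
| 0% | 23.8 | 0.999 | 22.5 | 0.967 |
| 10% | 21.4 | 0.856 | 20.2 | 0.665 |
| 20% | 19.0 | 0.423 | 18.0 | 0.259 |
| 30% | 16.6 | 0.109 | 15.8 | 0.056 |

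The right benchmark is the plan's own allowance. At exactly 20% attrition, p = 0.80 and P(≥20) = 0.617. With b = 10% and r = 10%, total attrition is 1 − 0.9 × 0.9 = 19%, which is inside the budget.

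**4. What follow-up after stopping does**

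Only stopped participants who are not assessed count in r. With b = 10% and 20% stopped, assessing half of them gives r = 10%, and the probability rises from 0.259 to 0.665. With 10% stopped and half assessed, r = 5%, p = 0.9 × 0.95 = 0.855, and it rises from 0.665 to 0.856. This holds only if an early-termination assessment counts as completed follow-up, which Section 9.3 does not say. MRI is scheduled only at baseline and completion (Section 6), so someone who stops without the Section 7.4 scan has no post-baseline value for the primary endpoints.

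**The case against.** Section 6.11 is a permissive list that does not claim to be complete, and Section 6.9.3 adds an approval step without exempting anyone from a stopping rule. An investigator who always follows Section 3.1 breaches neither. This stands, and it defeats one stronger reading: a reader might infer that the passages command opposite actions, but no passage says that a participant with a moderate reaction may continue. What remains is that the removal section omits the mandatory rule and treats as optional what other sections require.

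The mandatory rule speaks of reactions, while Section 6.11 and the dosing-approval sentence of Section 6.9.3 speak of events. If reactions are drug-related only, the overlap is narrower but not empty: the first three rows of the first table remain.

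A reader might also infer two conflicting severity scales. The documents do not reproduce ICH E2A, so they cannot show that it grades differently from Section 6.9.2. They show only that two sources are named.

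Finally, a reader might infer that the 20-completer target is broken. The documents do not support that. The rates are assumed, Section 7.4 offers assessments to those who stop, and Section 9.2 does not say that its 20% excludes safety stops. The protocol's statements that no toxicity called for dose exploration (Sections 1 and 3.2), and that there is no specific dose-limiting toxicity (Section 6.9.1), give no support for the higher rates.

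**Conclusion.** The concern holds as an unresolved inconsistency in the stopping provisions. For drug-related moderate or severe events, including serious ones graded at least moderate, one set of passages mandates discontinuation and another leaves it to judgement. The protocol does not state precedence, the scope of reaction, or whether discontinued refers to drug or trial. This rests on the text alone and needs no assumed rate.

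The consequence for the analysis is a risk, not a demonstrated loss. Its direction is clear: participants who tolerate the drug poorly are the ones who could leave the analysed set. Its size is unknown; the range in the working shows sensitivity and is not a forecast. The enrolment of 25 and the 20% allowance stand unless the sponsor finds that safety stops were left out. The point should be corrected because the remedy is cheap and bears on both participant safety and the analysed population.

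**What to change.** 1. Reconcile Sections 3.1, 7.3, 9.6, 6.9.3 and 6.11 into one discontinuation rule, stated once and cross-referenced. Its clinical content is for the sponsor to decide.
2. Say whether reaction means drug-related events only, and name one source for severity grading.
3. Separate stopping study drug from leaving the trial. For data collection, treat discontinuation as being from drug, with the participant remaining in follow-up unless consent is withdrawn.
4. State that the final MRI and cognitive assessments in Section 7.4 are sought from everyone who stops drug, as far as each is willing, and that these data are analysed in the Full Analysis Population. Amend the evaluable-participants sentence in Section 9.3 so that it does not exclude them.
5. Confirm in Section 9.2 that the 20% allowance includes safety stops under the rule chosen; revise it only if it does not.

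The cost is a wording amendment. No new procedure is needed, since Section 7.4 already provides for the assessments.
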